6.2 Subject Inclusion and Exclusion Criteria

6.2.1 Patient Inclusion Criteria

1. Each patient must satisfy at least one of the following criteria:

- a. The patient must have a clinically documented condition associated with CMV (e.g. interstitial pneumonia, hepatitis, retinitis, colitis)
Or
- b. The patient must have microbiological evidence of CMV viremia or tissue invasion as attested by viral culture, or detection of levels of CMV DNA in the blood or body fluids consistent with CMV infection.

2. Patient must also satisfy at least one of the following criteria:

- a. The patient's CMV infection is clinically progressing or CMV viremia is persistent or increasing (as evidenced by quantitation of CMV DNA in the blood) despite two weeks induction therapy with antiviral drugs.
Or
- b. The patient has developed CMV viremia as attested by viral culture, or detection of levels of CMV DNA in blood or body fluids while receiving prophylactic doses of antiviral drugs to prevent CMV infection post transplant.
Or
- c. The patient is unable to sustain treatment with antiviral drugs due to drug associated toxicities (e.g. myelosuppression [ANC < 1000/ μ l/ml without GCSF support] or nephrotoxicity [corrected creatinine clearance \leq 60 ml/min/1.73 m 2 or serum creatinine $>$ 2 mg/dl])

3. Patient has CMV specific T-cells from the donor of his/her HSCT available.

4. CMV infections are life threatening, and may involve multiple organ systems such as the lungs, liver, gastrointestinal tract, hematopoietic and central nervous systems. Antiviral drugs used for treatment may also compromise renal and hematopoietic function. Therefore, dysfunctions of these organs will not affect eligibility for this protocol.

5. Patients must meet the following clinical criteria to receive CMVpp65-CTL infusions

- a. Stable blood pressure and circulation, not requiring pressor support
- b. Evidence of adequate cardiac function as demonstrated by EKG and/or echocardiography.
- c. A life expectancy of at least 3 weeks, even if requiring artificial ventilation.
- d. There are no age restrictions

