11.0 TOXICITIES/SIDE EFFECTS

In this study, we will be capturing and tracking Grade 3-5 toxicities which occur within 30 days following an infusion of CMV infusion CTLs and are potentially attributable to treatment on study. We will also be capturing and tracking graft vs host disease occurring at any time point post-infusion. Patients who might subsequently receive donor lymphocytes, boosts, or a secondary transplant will be evaluable up until that time point. Toxicities which are attributable to underlying malignancy and/or were present prior to initiation of therapy will not be tracked. Please see section 17.2 for Serious Adverse Event reporting.

1. **Acute Toxicities and Transfusion Reactions.** The infusion of CMV-peptide specific T-cells might cause an acute transfusion reaction or an allergic reaction to the cell infusion manifested by any one or all of the following clinical signs and symptoms: fever, shaking chills, difficulty breathing, a drop in the blood pressure, skin rash or swelling of the mucus membranes in the mouth or vaginal tract, or impairment of kidney function. Based on prior experience with infusions of T-cells at our own and other

institutions, the risk of such immediate toxicities is anticipated to be small. However, each patient will be closely monitored for vital signs and clinical symptoms prior to and following T-cell infusion. Reactions will be treated as clinically indicated.

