2. **Specific Immune Reactions.** The CMV peptide-specific T-cells are expected to migrate to sites where CMV infected cells are concentrated, and to begin to kill these CMV infected cell populations. These cells may be concentrated in the lung, liver, retina/central nervous system, or intestinal tract. While it is expected that the small doses of T-cells administered will take time to replicate, and will exert their antiviral effects over a time period of days to weeks, it is possible that these cells could concentrate in an infected tissue and cause more severe inflammation as they attack virus infected cells. This could transiently increase the severity of a pneumonia or a CMV –induced encephalitis, retinitis, hepatitis or intestinal infection, and could even be life-threatening. Additionally, patients with pre-existing pulmonary conditions maybe at increased risk for development of pulmonary toxicity including diffuse alveolar hemorrhage. For patients treated for drug resistant CMV-retinitis, these T cells could potentially cause partial or complete blindness. If this were the case, immunosuppressive drugs might be required to halt such a reaction, and eliminate the T-cells. Were this required, the antiviral activity of the T-cells would be removed and the infection could progress in the absence of any specific resistance.

3. **Graft versus Host Disease.** The CMV peptide-specific T-cells have been cultured for over 4 weeks. During this time, T-cells reactive against other antigens, including alloantigens that might be expressed by tissues in the patient, die off and are deleted. The T-cells to be infused will be tested and shown to have no significant activity against normal allogenic cells prior to their infusion. However, there is a finite risk that small numbers of alloreactive T-cells could be transferred in the T-cell inoculum, which could cause Graft versus Host Disease (GvHD). This immune reaction against the host can cause skin rash, hepatitis, and enteritis. In its most severe form, it can be fatal. Were moderate to severe GvHD (Grade 2-4) to develop, the patient will be treated with high doses of glucocorticosteroids. Additional immunosuppressive agents may be used if the GvHD does not respond to steroid treatment.

4. **Infection.** There is a potential that transfusions of white cells or T-lymphocytes may also serve as vectors of serious infection. All precautions to maintain sterility will be taken.

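### Section 11.0 excludes toxicities present before therapy without a rule for worsening from baseline, so treatment-related worsening of existing CMV organ disease can be missed in the tracked toxicity data unless it is an SAE

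*Combined protocol and SAP*

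**What the plan says.** The opening paragraph of Section 11.0 contains two rules.

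- **Capture rule.** The study will be "capturing and tracking Grade 3-5 toxicities which occur within 30 days following an infusion" of the cells, provided that they "are potentially attributable to treatment on study".
- **Exclusion rule.** Toxicities that are put down to the underlying malignancy or that "were present prior to initiation of therapy will not be tracked". The sentence is silent on a toxicity that was present at a lower grade and then increases. The next sentence refers the reader to SAE reporting.

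Item 2 of the same section (Specific Immune Reactions) describes cells concentrating in infected tissue and inflaming it: "This could transiently increase the severity of a pneumonia or a CMV –induced encephalitis, retinitis, hepatitis or intestinal infection, and could even be life-threatening".

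Section 6.2.1 lets patients qualify through documented CMV disease of an organ (criterion 1a) or through virological evidence without organ disease (criterion 1b). Item 4 adds that, for the organ systems CMV or antiviral drugs may damage, "dysfunctions of these organs will not affect eligibility for this protocol".

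**The concern.** The hazard in Section 11.0 item 2 is, for a patient who enters with CMV organ disease, a worsening of something already there. The exclusion rule, taken at its word, removes conditions already there. So the sentence that limits data collection falls on some of the patients exposed to the risk that the same section describes.

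It also sits badly with the capture rule in its own paragraph. An attributable increase from Grade 2 to Grade 3 in an infected organ satisfies the capture rule and, read literally, is removed by the exclusion. The plan does not say which governs, and two data abstractors could record the same event differently.

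At stake is the completeness of the tracked Grade 3-5 data. Section 14.0 gives safety, alongside efficacy, as a purpose of the trial.

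**Working it through.** The plan states no figure on this point, so there is nothing to reproduce numerically. The check is to apply the written rules to cases and then see which other routes would record them. The grades below are illustrations. Every event is taken to fall within 30 days of an infusion and, where it is new or worse, to be potentially attributable to the cells.

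| Case | Capture rule (11.0) | Exclusion, read literally (11.0) | SAE route (17.3, 17.2.2) |
|---|---|---|---|
| CMV hepatitis, Grade 3 before and after infusion | No new event | Excluded | No new event |
| CMV hepatitis, Grade 2 rising to Grade 3, no seriousness criterion met | Tracked | Excluded | Not required |
| CMV pneumonia, Grade 2 rising to Grade 4, life-threatening | Tracked | Excluded | Must be submitted |
| Diffuse alveolar hemorrhage arising after infusion, absent before | Tracked | Not excluded | Must be submitted if serious |

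The first and last rows cause no difficulty. In the second and third rows the two rules of Section 11.0 give opposite answers. The third row still reaches the sponsor as an SAE; the second does not.

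Other places where the second-row event might be recorded:

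1. **Efficacy outcome, Section 12.0.** Progressive disease needs clinical and radiologic progression ascribable to CMV together with CMV DNA that is unchanged or higher. An inflammatory flare while CMV DNA falls does not meet that definition.
2. **Stopping rule, Section 14.0.** The boundaries are for acute GvHD of grades 3-4 and extensive chronic GvHD. No boundary counts organ flares.
3. **Organ monitoring, Section 10.0.** Oxygenation, imaging, eye examinations and stool measurements are scheduled for affected patients, so much of the raw information should exist. Nothing there requires a worsening to be counted as a toxicity.
4. **Removal from study, Section 13.0.** Related grade 3-4 toxicity is a possible ground for removal. That records a disposition for some patients; it does not define what is tracked.

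The plan does handle worsening for one pre-existing condition. Section 12.0 treats GvHD that was grade 1, or had resolved sufficiently, as worsened by the cells if grade 2 or higher appears 7 or more days after a dose. CMV organ disease has no counterpart to that rule.

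**The case against.** The strongest reply is that the serious form of this hazard is well covered. Section 17.3 (cited in Section 11.0 as 17.2) requires every SAE to be submitted, with grade and relationship to treatment. The definition in Section 17.2.2 includes death, life-threatening events, new or prolonged hospitalization, lasting incapacity and important medical events. It has no exemption for pre-existing conditions. This stands. A reader might infer from the exclusion that worsening of CMV organ disease is left out of the safety data altogether; the documents do not support that.

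Second, the exclusion has a natural benign reading: it may be meant for toxicities that stay as they were, such as the antiviral myelosuppression or nephrotoxicity that qualifies patients under Section 6.2.1, criterion 2c. On that reading a Grade 4 event arising after infusion was not present beforehand, and the capture rule applies. This is plausible, but the text does not say it, and the fix would only put that intent into words.

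Third, it would be wrong to say that the toxicity at risk is always present at baseline. Viremia alone qualifies for entry, and item 2 also names events that can be new, such as diffuse alveolar hemorrhage or blindness. This also stands, and it limits the point to patients entering with affected organs.

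Fourth, one might infer that SAE reports never contribute to the toxicity results. No section says so. Section 14.0 defines no toxicity table or rate, and Section 11.0 item 5 itself builds a rate (2 of 75 patients) from events it calls SAEs. The documents leave the link between SAE reports and tracked toxicities unstated.

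**Conclusion.** The point holds as a gap and an internal conflict in the data-capture rule. Section 11.0 gives no rule for worsening from baseline grade, its two sentences disagree on an attributable increase to Grade 3-5 in an already affected organ, and the literal reading conflicts with the hazard in item 2. The clearest loss is worsening that is Grade 3 and not serious; serious worsening should still reach the sponsor as individual reports, although the exclusion leaves unclear whether it also counts among the tracked toxicities.

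No numerical size can be attached. It would need the flare rate and the number of patients entering with overt organ disease, and the documents give neither. Section 3.0 describes acute toxicities in the phase I trial as rare, which argues against assuming a high rate. The conclusion rests on the wording alone and assumes that data staff would apply the exclusion as written.

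**What to change.** Keep the attribution condition and the exclusion of toxicities due to underlying malignancy. Replace the part of the sentence about pre-existing toxicities with:

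> Toxicities present before the first infusion are not tracked if they stay at or below their baseline grade. An increase from baseline grade to a higher grade within Grade 3-5, within 30 days of an infusion and potentially attributable to study treatment, is tracked, including in CMV-affected organs.

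Record a baseline grade for each pre-existing toxicity and affected organ from the pre-infusion examinations and laboratory tests in Sections 8.1 and 10.0, using the NCI scale named in Section 12.0. Because the study calendar restarts with each additional course, make clear that baseline means before the first infusion of the first course. Section 8.1 allows some tests to be omitted, so the form needs a code for baseline not assessed. For patients already treated, derive baseline grades from existing records where possible.

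The cost is a short amendment and one data field. No new visit or test is needed, and clinical management is unchanged. The downside is that reported toxicity counts may rise; retaining the attribution condition keeps clearly unrelated events out.

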11.1 Donor Toxicity/Side Effects

Risks of blood donation are minimal and include: minor discomfort at site of blood draw, some bleeding and/or bruising, and lightheadedness.

Risks of Leukapheresis include: The agent used to prevent clotting of blood during a leukapheresis may cause low levels of calcium in the blood and result in the lack of feeling or tingling of fingertips or around mouth, which normally last only a short time, and can, potentially, progress to cramps. This is normally treated with a calcium supplement.

Other leukapheresis side effects include:

- Pain

- Bruising at the needle insertion sites
- Dizziness
- Nausea
- Fainting due to temporary lowering of the blood pressure (rare)
- Infection (rare)

Platelet count may drop during the leukapheresis and will be measured after the collection. If platelet count falls enough to place the donor in danger of bleeding, count will be checked daily until it returns to normal.

The leukapheresis requires that a needle be placed in a vein in each arm. About 15% of the time, we are unable to use the donor's arm veins. The donor may be asked to go through a minor surgical procedure to place a central line. The donor will be asked to sign another consent form if a central line needs to be put in.

12.0 CRITERIA FOR THERAPEUTIC RESPONSE/OUTCOME ASSESSMENT

The primary endpoint of this study is to assess whether the infusion of the CMVpp65-CTLs has therapeutic activity in curing CMV infections in recipients of HSCT. This study specifically will evaluate the therapeutic efficacy and persistence after infusion of CMVpp65-CTLs derived from the HSCT transplant donor for the treatment of CMV infections. The second clinical end point of this study is the evaluation of GvHD induction after infusion of donor derived CMVpp65-CTLs. .

The responses of CMV infections will be clinically monitored as detailed under section 10. Responses to adoptively transferred T-cells are usually not observed until the T-cells have had time to expand within the transplant recipient, a period of at least 3 days, and as many as 18-21 days after the T-cell infusion. Accordingly, initial patient responses will be scored at weekly intervals, from day 7-day 21 post the initial infusion. Final responses will be captured in CRDB and scored between days 28-42 post the final infusion. Outcome responses will be captured post-first cycle and post final-cycle of infusions of CMV specific T cells. Best response observed in the full course of treatment will also be recorded as a distinct entity.

Clinical responses will be considered complete if all manifestations of CMV disease have resolved and/or the patient no longer has detectable CMV DNA by PCR.

A partial response will be defined as a $2 \times \log_{10}$ reduction in the level of CMV DNA detected in the patients blood and/or improvement in clinical parameters of CMV infection such that the patient is symptom-free.

Stable disease will be defined as no change in the clinic severity of disease in any organ.

Progressive disease will be defined as disease progression by clinical and radiologic parameters, ascribable to CMV infection in any affected organ, with unchanged or increased levels of CMV DNA.

Graft versus Host Disease initially developing after 10 days post T-cell infusion will be considered to be potentially ascribable to the T-cell infusion. Graft versus Host Disease will be diagnosed and clinically graded using the standard criteria of the IBMTR/NMDP Consensus Panel. Whenever, possible, the diagnosis will be confirmed by biopsy of skin or other involved organ, using the pathological criteria of Woodruff et al. Patients with preexisting GvHD of grade 1 severity not requiring

systemic steroids, or patients with a prior history of GvHD who have resolved this process sufficiently so that they no longer require parenteral steroid treatment will be considered to have developed an exacerbation or worsening of GvHD ascribable to the T-cell infusion if they redevelop clinical evidence of grade 2 or greater GvHD 7 or more days after a dose of T-cells.

For the evaluation of toxicities, the NCI Standard Toxicity Scale 4.0 will be employed.

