14.0 BIOSTATISTICS

A phase 2 trial design will be applied to determine the efficacy and safety of CMV specific T cells for the treatment of marrow transplant patients with CMV. The endpoint of this study is complete response, defined as the clearance of the CMV infection 3-7 weeks following completion of the last cycle of CMV CTLs. The evaluation of treatment efficacy will be assessed for patients receiving CMV specific T cells from their transplant donor. It is anticipated that accrual will be completed within 3 years.

A two-stage design with a maximum of 39 patients will be employed. The study design discriminates between population response rates of 0.50 and 0.70. In the first stage, 23 patients will be enrolled in the study. If 11 or fewer complete responses (CRs) are observed, then the trial will be stopped. If at least 12 complete responses are observed, then 16 additional patients will be accrued. At the conclusion of the trial, if 23 or fewer CRs are observed, we will conclude that the treatment is not sufficiently active. This design has power 0.90 for a population CR rate equal to 0.70 using a one-sided test with type 1 error equal to 0.10.

The probability of a complete response and the proportion of patients requiring ganciclovir or foscarnet will be computed.

Following approval of Amendment 22, additional accrual on study is anticipated to be 2-3 patients per year, for an additional 3 years, for a target accrual of approximately 7 additional patients. As the accrual will be lower than the originally targeted accrual number, there will be no hypothesis test for efficacy analysis and the efficacy analysis is to estimate the complete response (CR) rate with its 80% confidence interval. For example, with 9 CR observed among a total of 15 subjects, the estimate of CR rate is 60% with the 80% Clopper-Pearson exact confidence interval of (40.4%, 77.4%).

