The effects of infusing activated CMV-specific T-cells on the general immune function of the host will be assessed by recording CD4⁺ and CD8⁺, CD3⁺ T-cells, NK cells and B-cells prior to and one week following each course of cell infusions and 1, 2 and 4 months following completion of the second course of cells. In addition, the levels of CMV DNA and T cells generating IFNg in response to the CMV pentadecapeptides will be measured weekly for the first 8 weeks and then monthly until 6 months post infusion. Nonparametric smoothing will be used to estimate the population trajectory of these response curves over time. In addition, a generalized estimating equation approach will be used to model the relationship between the immunologic reconstitution factors and complete response.

In order to reduce patient risk, the study design includes early termination in the event of excessive graft versus host disease during the accrual period. The stopping rule for excessive GvHD and the corresponding power calculation will be applied separately for the two donor groups. In the event that the stopping boundary is crossed for one of these groups, the study will continue accrual in the other group.

Allo donor

Failure type	# of failures needed to stop the study	Failure rate in the population	Probability boundary is crossed
Acute GvHD (grades 3-4)	3 within the first 15 patients	0.06	0.10
	4 within the first 24 patients		0.90
	5 within the first 35 patients	0.20	
	6 within 39 patients		
Chronic GvHD (extensive)	3 within the first 15 patients	0.06	0.10
	4 within the first 24 patients		0.90
	5 within the first 35 patients	0.20	
	6 within 39 patients		

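### Does the lack of a planned GvHD estimate in Section 14.0 leave the second primary objective unanswerable?

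*Combined protocol and SAP*

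**What the plan says.** Section 2.0 lists two primary objectives: therapeutic activity, and the risk that the cells cause GvHD or make it worse. Section 12.0 repeats the second: "The second clinical end point of this study is the evaluation of GvHD induction after infusion of donor derived CMVpp65-CTLs".

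Section 14.0 is narrower. It states "The endpoint of this study is complete response, defined as the clearance of the CMV infection", and names what will be calculated: "The probability of a complete response and the proportion of patients requiring ganciclovir or foscarnet will be computed". Since Amendment 22 there is no efficacy test, and "the efficacy analysis is to estimate the complete response (CR) rate with its 80% confidence interval". The worked example is "with 9 CR observed among a total of 15 subjects". GvHD enters only through monitoring: "the study design includes early termination in the event of excessive graft versus host disease during the accrual period". The table there counts severe acute disease (the row labelled "Acute GvHD (grades 3-4") and extensive chronic disease.

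Other sections say how GvHD is observed:

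- **Section 11.0** has GvHD tracked at any time after infusion, with evaluability ending at donor lymphocytes, a boost or a second transplant.
- **Section 12.0** requires grading by IBMTR/NMDP consensus criteria and gives two attribution rules. For new disease, "Graft versus Host Disease initially developing after 10 days post T-cell infusion will be considered to be potentially ascribable". For patients with mild or resolved earlier GvHD, the rule is grade 2 or higher from 7 days after a dose.
- **Section 10.0** marks an examination that includes GvHD assessment through Month 6. Its footnotes give weekly GvHD assessment to Week 8, a Day 100 consensus, and a calendar restart for each extra course.

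**The concern.** Read alone, Section 14.0 gives a primary objective no rate, denominator, window or interval. A boundary that was not crossed is not an estimate of risk.

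The sections that might fill the gap name different grades: none for new disease and grade 2 or more for worsening (Section 12.0), and grades 3-4 in the stopping table (Section 14.0). They also name different times: Week 8, Day 100, Month 6 and any time. A new grade 2 case falls under Section 12.0 but not under the stopping rule.

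If the team chose the grade and window after seeing the data, one set of patients could yield quite different headline rates. In a small single-arm trial with no comparator, that could change how safe the product appears.

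**Working it through.** **1. Stopping rule, from the Section 14.0 table.** The boundaries are 3 of 15, 4 of 24, 5 of 35 and 6 of 39, at failure rates 0.06 and 0.20. The crossing probability is the sum over looks of P(count reaches the boundary at this look and at no earlier one), with binomial increments between looks.

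| True rate | Stated | Recomputed |
|---|---|---|
| 0.06 | 0.10 | 0.101 |
| 0.20 | 0.90 | 0.896 |

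Both reproduce. Checking after every patient gives the same values as checking only at the four sizes.

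**2. The same rule if accrual ended at 15.** P(cross) = 1 − P(0) − P(1) − P(2) for a binomial count with n = 15.

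- Rate 0.06: 1 − 0.395 − 0.378 − 0.169 = 0.057 (from unrounded terms).
- Rate 0.20: 1 − 0.035 − 0.132 − 0.231 = 0.602.

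At a true rate of 20% the boundary would go uncrossed with probability 1 − 0.602 = 0.398. So an uncrossed boundary is weak evidence at this size. The plan does not offer it as an estimate.

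**3. The plan's interval method.** For x events in n, the 80% Clopper-Pearson limits are the 0.10 quantile of Beta(x, n − x + 1) and the 0.90 quantile of Beta(x + 1, n − x). For 9 of 15 this gives 40.4% to 77.4%, as stated in Section 14.0.

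**4. The same method applied to GvHD at n = 15.** With no events the upper limit is 1 − 0.10^(1/15) = 14.2%.

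| Events | Rate | 80% interval |
|---|---|---|
| 0 | 0% | 0 to 14.2% |
| 1 | 6.7% | 0.7 to 23.6% |
| 2 | 13.3% | 3.6 to 31.7% |
| 4 | 26.7% | 12.2 to 46.4% |

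The data the protocol already collects are enough for this.

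**5. Does the choice of grade matter?** Assume, for illustration, no grade 3-4 event and one new grade 2 event in 15. The stopping-rule category gives 0/15 and a grade 2 or higher category gives 1/15. A table by grade shows both lines, so the analyst need not choose one.

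**6. Do the grades conflict?** Section 12.0 says when GvHD may be ascribed to the cells, and its two rules cover different patients (new onset, and mild or earlier disease). Section 14.0 says when severe GvHD halts accrual, and a stopping rule may properly be narrower than an outcome table. Section 4.3 (a historical threshold for a T-cell dose) and Section 11.0 (when GvHD is treated) also name grades, but they do not define an analysis.

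**7. Do the windows conflict?** Section 11.0 sets how long events count; Section 10.0 sets visits. Week 8 is day 56 and Month 6 is 6 × 30.44 = day 183, both inside open-ended capture. If a second course starts at about day 21 + 21 = 42 (Section 9.1, Treatment with CMVpp65 Specific T-cells), its Month 6 falls at about 183 + 42 = day 225, which open-ended capture also covers.

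**The case for a change.** The strongest case for a change is that this is a primary objective, not a side observation. Amendment 22 moved efficacy from testing to estimation with an interval and gave GvHD nothing equivalent. The stopping table's 0.90 assumes 39 patients, against 0.602 at 15. One sentence would cost little and would settle event and window before the final analysis.

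Much of this stands. Section 14.0 is silent on a GvHD summary, and the origin of Day 100 is not given.

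Two parts do not stand. The first is that the choice of grade decides whether the result excludes 20%. The 0.20 in the stopping table belongs to acute grade 3-4 and to extensive chronic GvHD, each taken separately. It is no yardstick for grade 2 or any-grade rates, and nothing in the protocol requires the final result to exclude it.

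The second is that a detailed prescription would clearly be better. Ending at Month 6 from the first course passes over the one GvHD-specific consensus point, Day 100. It also drops days 183 to 225 of follow-up after a second course. Keeping patients whose evaluation ended early in a simple denominator pulls a safety rate down. Making attribution secondary sits poorly with an objective about GvHD caused by the transfer. These choices are debatable and correct no error.

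**Conclusion.** No change to the plan follows. The gap is real, but it is one of detail that a competent analyst fills from the protocol itself: new and worsened GvHD by grade, among infused patients, with the exact 80% interval already in use.

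Precision would be poor under any wording. With no events the upper limit is 14.2% at 15 patients, 9.9% at an assumed 22, and 5.7% at 39. Fuller text would not narrow these limits.

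The conclusion rests on three assumptions: GvHD is captured and graded as Sections 11.0 and 12.0 require; the report shows all grades, not one selected category; and 15 is only the example size, since the final total is not stated. Severe GvHD remains under the stopping rule, whose stated probabilities are correct for 39 patients.
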